17.2 Estimated glomerular filtration rate

If serum creatinine (SCr) is measured with routine methods that have not been recalibrated to be traceable to isotope dilution mass spectrometry (IDMS) (e.g. the traditional Jaffé reaction), the eGFR should be obtained from the original Schwartz formula: ⁽¹²⁾

$$\text{eGFR (mL/min/1.73 m}^2\text{)} = k * \text{height (cm)} / \text{SCr (mg/dL)}$$

Where k is proportionality constant:

k = 0.55 in children up to 13 years of age

k = 0.70 in boys >13 years and <18 years of age (not in girls; because of the presumed increase in male muscle mass, the constant remains 0.55 for girls)

If SCr is measured by an enzymatic creatinine method that has been calibrated to be traceable to IDMS, the updated Schwartz formula should be used to obtain the eGFR: ⁽¹³⁾

$$\text{eGFR (mL/min/1.73 m}^2\text{)} = 0.413 * \text{height (cm)} / \text{SCr (mg/dL)}$$

The National Kidney Disease Education Program website (http://www.nkdep.nih.gov/professionals/gfr_calculators/index.htm) offers electronic calculators of eGFR in the pediatric population based on the updated Schwartz formula.

Note: To express SCr in micromoles per liter, the value should be multiplied by 88.4 (1 mg/dL = 88.4 μmol/L).

Rivaroxaban (BAY-59-7939, JNJ-39039039) is being co-developed under a collaboration and license agreement between Bayer HealthCare AG (BHC) and Ortho McNeil Pharmaceuticals, Inc. (OMP) dated 01 Oct 2005. As determined by the parties, both BHC and Janssen Pharmaceuticals Inc. (successor in interest to OMP) may use affiliated corporate entities to conduct this clinical study. With regard to Janssen Pharmaceuticals Inc., such affiliates may include Janssen Research & Development, LLC (formerly Johnson & Johnson Pharmaceutical Research & Development LLC), Janssen Scientific Affairs, LLC, and Janssen-Cilag International N.V. The term “sponsor” or “designee” is used to represent these various legal entities that have been identified to perform various clinical study services; the actual sponsor or designee is identified on the Contact Information page that accompanies this protocol.

1. Introduction

This SAP is based on the Clinical Study Protocol version 1.0 (04 Mar 2014), Global Amendment 1 (forming Integrated Protocol version 2.0, dated 02 Sep 2014), Local Amendment 2 (applicable to Japan only) to Clinical Study Protocol (21 Oct 2014), Local Amendment 3 (applicable to Canada only) to Clinical Study Protocol (28 Oct 2014), Global Amendment 4 (forming Integrated Protocol version 3.0, dated 14 Apr 2015), Local Amendment 5 (applicable to Canada only) to Clinical Study Protocol (16 Jun 2015).

“The goal of the rivaroxaban pediatric program is to make rivaroxaban available to children for treatment and secondary prevention of venous thromboembolism. To accomplish this goal, it will be necessary to evaluate a pediatric age- and body weight adapted dosing regimen, and to address the safety and efficacy of rivaroxaban.”

For more details see Integrated Protocol, [Section 1](#).

2. Study Objectives

The primary objective is:

- to assess the incidence of major bleeding and clinically relevant non-major bleeding

The secondary objectives are:

- to assess the incidence of recurrent symptomatic venous thromboembolism
- to assess asymptomatic deterioration in the thrombotic burden on repeat imaging
- to characterize the pharmacokinetic/pharmacodynamic profile of a 30-day treatment with oral rivaroxaban.

3. Study Design

This is a single-arm, multicenter study evaluating the safety, efficacy and PK/PD profile of a 30-day treatment with age- and body weight-adjusted oral rivaroxaban in children aged between 6 months and < 6 years with various manifestations of symptomatic and asymptomatic venous thrombosis (Comparator arm was removed via Amendment 4; up to Protocol Amendment 4 it was an active-controlled randomized study).

The treatment period will be followed by a 30-day post study treatment period, regardless of the duration of study drug administration. After cessation of study treatment, it is at the investigator's discretion to continue with anticoagulants.

For further details see Integrated Protocol, [Section 3](#).

3.1 Study population

Twenty children (10 per age group) are planned to be treated with rivaroxaban in total according to Protocol Amendment 4. Enrolment will start with the 2 to < 6 year age group, followed by the 6 months to < 2 year age group upon availability of the age and body weight

adapted dosing regimen for the age group 6 months to < 2 years (before Protocol Amendment 4 forty children; 20 per treatment group were planned to be enrolled and randomized to either rivaroxaban or standard of care).

Children who have been treated for at least 2 months or in case of catheter-related thrombosis, treated for at least 6 weeks with LMWH, fondaparinux and/or VKA for symptomatic or asymptomatic venous thrombosis will receive age- and body weight-adjusted rivaroxaban. Before first study treatment administration, the documented index thrombotic event will be confirmed by the central adjudication committee (CIAC) for the child to be eligible for the study. For further details see Integrated Protocol, [Sections 3](#) and [4](#).

3.2 Treatment regimen

In this study, only rivaroxaban will be used after Protocol Amendment 4. Allocation to treatment will be done centrally by an interactive voice/web response system (IxRS; before Protocol Amendment 4 allocation was to be stratified by baseline presentation of venous thrombosis and it was to be done in a 1:1 ratio for rivaroxaban: standard of care, separately by age groups). The IxRS will initially restrict enrollment to children in the age group between 2 and less than 6 years. Once the age-and body weight adjusted dosing regimen has been confirmed for the age group 6 months to < 2 years, the IxRS will allow enrollment for this age group as well.

For further details see Integrated Protocol, Sections 3 and 5.

3.3 Outcomes

- The primary safety outcome is the composite of major bleeding and clinically relevant non major bleeding.
- Other safety outcomes:
 - all deaths
 - other vascular events (myocardial infarction, cerebrovascular accident, non-CNS systemic embolism).
- Efficacy outcomes:
 - Symptomatic recurrent VTE (composite of DVT and fatal or non-fatal PE)
 - Composite of symptomatic recurrent VTE and asymptomatic deterioration on appropriate imaging test

All index venous thrombotic events, and all suspected recurrent venous thromboembolic events, asymptomatic deterioration in the thrombotic burden on repeat imaging, bleeding, other vascular events and deaths that occur after visit 2 including the 30 day post treatment period, will be evaluated by a CIAC, which will be provided with all relevant documentation related to the events. Adjudication results will be the basis for the final analyses.

For further details see Sections [6.8](#), [6.11](#) and [6.14.2](#) of the Integrated Protocol as well.

4. General Statistical Considerations

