Inclusion/exclusion criteria (continued)	10. Concomitant use of strong inducers of CYP3A4, i.e. rifampicin, rifabutin, phenobarbital, phenytoin and carbamazepine 11. Hypersensitivity or any other contraindication listed in the local labeling for the experimental treatment 12. Inability to cooperate with the study procedures 13. Previous enrollment to this study 14. Participation in a study with an investigational drug or medical device within 30 days prior to Visit 2. ¹³
Primary outcome	Composite of major and clinically relevant non-major bleeding
Secondary outcome	Composite of all recurrent venous thromboembolism and asymptomatic deterioration on repeat imaging; results of pharmacokinetics (PK) / pharmacodynamics (PD).
Statistical Analysis Plan	
The incidence of the composite of major and clinically relevant non-major bleeding and the incidence of symptomatic recurrent venous thromboembolism, and asymptomatic deterioration in the thrombotic burden on repeat imaging will be summarized descriptively.
 
Quantitative data will be described by summary statistics and presented by age.
 
Results of PK/PD analyses will be assessed descriptively. ¹⁴

¹³ Comparator arm was removed via Amendment 4 (see Section 16.2.2.2)

¹⁴ Statistical Analysis Plan modified via Amendment 4 (see Section 16.2.2.2)

Figure 1–1: Flow chart

	Screen ^a	Treatment period			30 day post study treatment contact	
Visit	1	2	3	4	5	
Days	Day -60 to Day -10	Day 1	Day 15 ± 5 days	Day 30 ± 3 days	Day 60 ± 7 days	
Obtain informed consent	•					
Check in-/exclusion criteria	•					
Obtain demographic data	•					
Check medical history	•	•				
Record anticoagulant medication	•	•				
Obtain height/length, and blood pressure	•					
Obtain body weight	•	•				
Check Hb, platelets, creatinine, ALT, bilirubin		• ^b				
Send baseline adjudication package	•					
Review the CIAC decision for index thrombotic event for final eligibility ^c		•				
Re-confirm in-/exclusion criteria ^c		•				
Provide patient details to IxRS	•					
Dispense study medication		•				
Instruct how to take study medication		•				
Provide study booklet		•				
Provide Rivaroxaban Oral Suspension Handling Guidelines to parents		•				
Record all concomitant medication		•	•	•	•	
Check for study outcomes ^d			•	•	•	
Check adverse events		•	•	•	•	
Check Hb, platelets, ALT, bilirubin				•		
Check drug accountability and compliance ^e			•	•		
Repeat imaging and send adjudication package				•		

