6.11 Efficacy outcome

The efficacy outcome will be symptomatic recurrence of venous thrombosis or asymptomatic deterioration.

Symptomatic recurrence of venous thrombosis or asymptomatic deterioration should be documented using the appropriate imaging test.

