6.3 Efficacy

All efficacy analyses will be performed on the full analysis set population based on the outcomes confirmed by the CIAC. Incidence proportions will be calculated for the efficacy outcomes (see Section 3.3) overall and by age stratum for the rivaroxaban group and for the standard of care group (randomized before Protocol Amendment 4) separately. The analyses described above will include events up to the end of intended study treatment (30 days after study medication assignment) regardless of the actual stop date of study medication.

In addition if there is at least one confirmed recurrent event in the corresponding time period, the analyses described above will be performed counting only events that occurred during study treatment or within 2 days after stop of study medication (i.e. treatment-emergent) on the safety population as well.

Proportion of events that occurred more than 2 days after stop of study medication up to 30 days will be described (denominator: number of subjects entering the observational period) if there is at least one confirmed recurrent event in the corresponding time period.

In addition, all descriptive efficacy analyses will be performed on the per protocol population as a supportive analysis.

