6.3.1 Sensitivity analysis to account for dropouts

Sensitivity analyses will be performed if at least one confirmed recurrent event occurred within the 30 days intended treatment period in order to evaluate the potential influence of dropouts on the incidence of the primary efficacy outcome for the treatment period up to visit 4. In these analyses subjects with premature termination before visit (no follow-up until Day 30) will be assumed as having hazard of recurrence of VTE (primary efficacy outcome) 1.5 times (scenario 1) and twice (scenario 2) as high as the hazard calculated including all patients within each treatment group assuming informative censoring. For this sensitivity analysis exponential distribution for the event rates (hazard) will be assumed and the analysis will be performed for the rivaroxaban treatment group. This method is an application of methods for informative missingness odds ratio (IMOR) by White et al (5).

- $t_j \sim \exp(h_{\text{non-informative}})$
 $P_{\text{non-informative}} = 1 - e^{-(30 \cdot h_{\text{non-informative}})}$
 $h_{\text{dropout}} = h_{\text{non-informative}} \cdot \text{IMHR}$
 $P_{\text{overall}, j} = 1 - e^{-(t_j \cdot h_{\text{non-informative}} + [30 - t_j] \cdot h_{\text{dropout}})}$
 $P_{\text{overall, mean}} = \text{mean}(P_{\text{overall}, j})$

where

t_j : event times (or censoring) of patient j .

$h_{\text{non-informative}}$: hazard of the primary efficacy outcome assuming non-informative censoring using all patients' data.

$P_{\text{non-informative}}$: the cumulative event probability at Day 30 based on the exponential model.

h_{dropout} : hazard of the primary efficacy outcome after dropping out.

$P_{\text{overall}, j}$: cumulative event probability at Day 30 calculated based on mixture of $h_{\text{non-informative}}$ up to drop out and h_{dropout} from drop out up to Day 30 using exponential model for patient j .

$P_{\text{overall, mean}}$: mean of the cumulative event probability.

IMHR: informative missingness hazard ratio.

- Prior for log hazard (non-informative censoring):
 $\log(h_{\text{non-informative}}) \sim \text{dnorm}(-6.6, 1/\sqrt{0.4})$.
- Priors (informative) for IMHR:
IMHR $\sim \ln N(\mu, \sigma)$ where
 $\mu = \text{scenario 1: } \ln(1.5) = 0.405$; scenario 2: $\ln(2) = 0.693$ and
 $\sigma = 1/\sqrt{10} = 0.316$.

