6.6 Pre-specified subgroup analysis

6.6.1 Analysis by baseline characteristics

The baseline, efficacy, bleeding and safety analyses will be done by age cohort and by baseline presentation of venous thrombosis as described in sections [6.1](#), [6.2](#), [6.3](#), [6.5.1](#).

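### SAP 3.3 spells out symptomatic recurrent VTE as DVT plus PE, while the protocol outcome sets no site limit; taken literally, confirmed recurrences at other eligible sites would not be counted

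*SAP*

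**What the plan says.** SAP 3.3 lists two efficacy outcomes. The first is "Symptomatic recurrent VTE (composite of DVT and fatal or non-fatal PE". The second combines that same term with asymptomatic deterioration on imaging. SAP 6.3 takes its outcomes from this list: "Incidence proportions will be calculated for the efficacy outcomes (see Section 3.3) overall and by age stratum".

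Elsewhere no site limit is stated:

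- Protocol 6.11: "The efficacy outcome will be symptomatic recurrence of venous thrombosis or asymptomatic deterioration".
- Protocol synopsis, secondary outcome: "Composite of all recurrent venous thromboembolism and asymptomatic deterioration on repeat imaging".
- SAP 2, secondary objectives: "to assess the incidence of recurrent symptomatic venous thromboembolism".

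The eligible index events are listed in the protocol synopsis (Indication) and in Protocol 1.2. Both use the term deep vein thrombosis only for the lower and upper extremity. Both give separate entries to caval, right atrial, subclavian, jugular, cerebral vein and sinus, mesenteric, portal and renal thrombosis.

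SAP 3.3 also sends every suspected recurrent event to the central independent adjudication committee (CIAC), bases the final analyses on its results, and refers to Protocol 6.11 for detail.

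**The concern.** The parenthesis in SAP 3.3 is operative text. It is the only place where the SAP names the components of symptomatic recurrent VTE, and SAP 6.3 builds its incidence proportions on it. A programmer who follows it would count DVT and PE and nothing else, whereas one who follows Protocol 6.11 would count a recurrence at any venous site. In adults with limb DVT or PE the two readings would rarely differ. Here they can, because children with cerebral, portal, renal and other thromboses are eligible by design.

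At stake is whether a confirmed symptomatic recurrence appears in the efficacy tables. In a study of about 20 children, a single event decides whether the reported incidence is zero.

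**Working it through.** **Step 1. Definitions side by side.** The table asks whether each type of CIAC-confirmed event enters the numerator, with DVT read as the indication list uses it.

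| Confirmed event | Protocol 6.11 | SAP 3.3, first outcome | SAP 3.3, second outcome |
|---|---|---|---|
| Symptomatic DVT of a limb | yes | yes | yes |
| Symptomatic PE | yes | yes | yes |
| Symptomatic portal vein or cerebral sinus recurrence | yes | no | no |
| Asymptomatic deterioration at the portal vein or a cerebral sinus | yes | not a component | yes |

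The third row is the conflict. The second SAP outcome does not rescue the event, because it reuses the narrow term and adds only asymptomatic deterioration.

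**Step 2. How many listed sites are involved.** The synopsis gives 11 site entries: lower-extremity DVT, caval, right atrial, PE, upper-extremity DVT, subclavian, jugular, cerebral vein and sinus, mesenteric, portal and renal. Catheter-related thrombosis is a further entry, but it is not a site. Protocol 1.2 has the same 11. Three are named DVT or PE, so 11 − 3 = 8 are not. This counts labels in a list. It says nothing about how often recurrences occur there, and the documents give no distribution of index sites.

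**Step 3. The plan's own intervals.** SAP Table 9-1 gives exact Blyth–Still–Casella limits for n = 20.

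- Lower limits: exact binomial acceptance regions of minimum length give 0.0%, 0.26%, 1.82%, 4.22% and 7.14% for 0 to 4 events. These match the table's 0.0, 0.3, 1.8, 4.2 and 7.1. For one event, for example, 1 − 0.95^(1/20) = 0.26%.
- Upper limits: minimum-length regions are not unique. They allow 14.3% to 17.7% for 0/20 and 22.2% to 25.6% for 1/20. The table's 15.4% and 23.1% lie inside these ranges. Casella's specific refinement was not reproduced, so the upper limits below are taken from the table.

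**Step 4. Illustration: one omitted event.**

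- All 20 children: 1/20 = 5.0% (0.3% to 23.1%) becomes 0/20 = 0% (0.0% to 15.4%). The upper limit falls by 23.1 − 15.4 = 7.7 percentage points.
- Within one age group of 10: 1/10 = 10.0% becomes 0/10 = 0%.

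The denominator of 20 is the planned number of treated children. Efficacy is analysed on the full analysis set, which may be slightly larger.

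**The case against.** The strongest reply is that nobody meant to narrow the outcome. Much of the text supports this. The CIAC sees all suspected recurrent events, and its results are the basis of the analyses. SAP 3.3 points to Protocol 6.11. DVT carries no limb qualifier in SAP 3.3, whereas the indication list adds one when a limb is meant. Protocol 7.1 requires revisions to be clearly identified in the final SAP, and the change list in SAP 7 declares no narrower outcome. Counting asymptomatic deterioration of a portal thrombus but not a symptomatic recurrence there would be an odd rule. The parenthesis has the same components as the adult outcome described in Protocol 1.3, so wording carried over from the adult programme is plausible, though not documented.

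This makes the broad intent likely, but it does not settle the numerator. Adjudication decides which events are confirmed, not which confirmed events belong to an outcome spelled out as DVT and PE. A pointer for further detail leaves two definitions standing.

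A reader might infer more than the documents support:

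- **That the conditional analyses would be lost.** SAP 6.3 makes further analyses conditional: "In addition if there is at least one confirmed recurrent event in the corresponding time period". SAP 6.3.1 does likewise: "Sensitivity analyses will be performed if at least one confirmed recurrent event occurred within the 30 days intended treatment period". Neither condition carries a site limit, so on its face a confirmed portal recurrence would meet it. Losing these analyses would need a second narrow reading. The point is only a reason to use one definition throughout.
- **That the event would also vanish from adverse event reporting.** Protocol 7.9.1.1 exempts an event only if it is already captured as an outcome in the eCRF, so an event not captured there gains no exemption from that section. Any tension with Protocol 7.9.7, which keeps recurrent venous thrombosis out of (S)AE reporting, lies within the protocol and exists whatever SAP 3.3 says.
- **That results by baseline presentation would be distorted.** SAP 6.6.1 says "The baseline, efficacy, bleeding and safety analyses will be done by age cohort and by baseline presentation of venous thrombosis" but refers to 6.3 for the efficacy method, and 6.3 describes only overall and age-stratum results. Those rows are not specified clearly enough to support a claim.

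**Conclusion.** The concern holds as a conflict of definitions. The components stated in SAP 3.3, on which the SAP 6.3 incidences rest, are narrower than the outcome in Protocol 6.11, the synopsis and SAP 2. Followed literally, a confirmed symptomatic recurrence at any of the eight separately listed sites would be left out of both efficacy outcomes.

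The documents do not support the stronger inferences that the outcome was deliberately restricted or that events will be lost. Each such event would lower the count by one. Its effect on a sole event is shown in the illustration, which assumes 20 children, and no expected number of events can be derived from the documents. The affected results are secondary and descriptive, with no test or decision rule. The primary bleeding outcome and the sample size are untouched. The wording should still be settled before analysis, because two competent analysts could count differently.

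**What to change.** In SAP 3.3, replace the parenthesis with the protocol's definition: any CIAC-confirmed symptomatic recurrent venous thrombosis at any site in the indication list, including fatal or non-fatal PE. State in 6.3 and 6.3.1 that a confirmed recurrent event has this same definition.

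The cost is one SAP sentence and a cross-reference in two sections, with no new data collection. The reported incidence may be slightly higher than under a DVT and PE count. If the sponsor also wants that narrower count, a listing of confirmed recurrences by site would supply it.

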⁵ Comparator arm was removed via Amendment 4 (see Section 16.2.2.2)

Indication	Young children with documented venous thrombosis, including deep vein thrombosis of the lower extremity, caval vein thrombosis, right atrial thrombosis, pulmonary embolism, deep vein thrombosis of the upper extremity, subclavian vein thrombosis, jugular vein thrombosis, and cerebral vein and sinus thrombosis, mesenteric vein thrombosis, portal vein thrombosis, renal vein thrombosis or catheter-related thrombosis
Diagnosis and main criteria for inclusion	Children aged 6 months to < 6 years with documented symptomatic or asymptomatic venous thrombosis treated for at least 2 months or, in case of catheter-related thrombosis, treated for at least 6 weeks with LMWH, fondaparinux and/or VKA. ⁶ The imaging of the index thrombotic event will be confirmed by the central independent adjudication committee (CIAC).
Study design	Single-arm, multicenter study ⁷
Methodology	Children will receive rivaroxaban according to an age- and body weight-adjusted regimen. The study treatment period is for a total of 30 days followed by an observational period of another 30 days. All suspected clinical study outcomes and baseline and repeat thrombosis imaging tests will be assessed by a CIAC. An independent data monitoring committee (DMC) will monitor the children's safety and give recommendations to the steering committee. ⁸
Number of children	20 children (10 per age group) treated with rivaroxaban. ⁹

⁶ Inclusion criteria modified via Amendment 4 (see Section 16.2.2.2)

⁷ Title was modified via Amendment 4 (see Section 16.2.2.1)

⁸ Comparator arm was removed via Amendment 4 (see Section 16.2.2.2)

⁹ Total number of subjects was reduced via Amendment 4 (see Section 16.2.2.2)

Inclusion/exclusion criteria	Inclusion

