7.5 Efficacy analysis - amended

All efficacy analyses will be performed on the FAS population. The occurrence of recurrent venous thromboembolism and asymptomatic deterioration in thrombotic burden will be summarized by age group.⁴⁹

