6.2 Bleeding analysis

All bleeding analyses will be performed on the safety analysis set based on the outcomes confirmed by the CIAC. Bleeding events that occurred during study treatment or within 2 days after stop of study medication (i.e. treatment-emergent) will be summarized. Bleeding events observed more than 2 days after stop of study medication will be described separately. Individual listings of major and clinically relevant non-major bleeding events will be provided.

Incidence proportions (number of children with outcome by number of children at risk at start of study medication) will be presented for the primary safety outcome, for major bleedings, for all confirmed bleedings and components for pooled data and for each age stratum and by baseline presentation of venous thrombosis for the rivaroxaban group and for the standard of care group (randomized before Protocol Amendment 4) separately.

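### Asymptomatic deterioration on repeat imaging is a stated secondary objective, but the SAP gives it no result of its own, and its composite would count unscanned children as event-free

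*SAP*

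**What the plan says.** The objective is listed separately from symptomatic recurrence in both documents: "to assess asymptomatic deterioration in the thrombotic burden on repeat imaging" (SAP section 2; same objective in Protocol section 2). Protocol 7.5 carries it into the analysis: "The occurrence of recurrent venous thromboembolism and asymptomatic deterioration in thrombotic burden will be summarized by age group".

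SAP 3.3 names two efficacy outcomes. One is "Symptomatic recurrent VTE (composite of DVT and fatal or non-fatal PE"). The other is the "Composite of symptomatic recurrent VTE and asymptomatic deterioration on appropriate imaging test". SAP 6.3 then states that "Incidence proportions will be calculated for the efficacy outcomes (see Section 3.3) overall and by age stratum", on the full analysis set, which SAP 5.1 defines as all enrolled children except screening failures. SAP 6.3 does not mention components. The bleeding section, SAP 6.2, does: it plans results "for all confirmed bleedings and components for pooled data".

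On the scans themselves, the Protocol synopsis says that "baseline and repeat thrombosis imaging tests will be assessed by a CIAC". Protocol 6.1 and 6.5 make the repeat scan conditional: ultrasound where applicable, MR only if no sedation or anaesthesia is needed, and CT or contrast angiography only if already planned outside the study. The Visit 4 list for a child who stopped treatment early does not include repeat imaging. SAP 4.3 plans a count of missing repeat imaging tests. That is the only other planned summary of repeat imaging in the SAP.

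**The concern.** A stated objective should lead to a result that a reader can find. Here the chain runs from objective to Protocol 7.5 and then stops: the SAP outcome list replaces deterioration with a composite that contains it.

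The denominator is the larger problem. Symptomatic recurrence can be ascertained in every child who is followed. Asymptomatic deterioration can be seen only on a scan. Placing both in one proportion on the full analysis set treats a child with no scan the same as a child whose scan showed no deterioration. The SAP has no rule for this case: the sensitivity analysis in SAP 6.3.1 concerns children without follow-up to Day 30, not children who were followed but not imaged.

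At stake is how much reassurance a low count gives. Protocol 1.3 makes further studies depend on the regimen being safe and showing no evidence of lost efficacy. A proportion diluted by unscanned children overstates how firmly deterioration has been excluded.

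**Working it through.** **1. Trace the objective.**

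| Step | Symptomatic recurrence | Asymptomatic deterioration |
|---|---|---|
| Protocol 2, SAP 2 (objectives) | listed | listed separately |
| Protocol 7.5 (analysis) | to be summarised | to be summarised |
| SAP 3.3 (outcomes) | alone and in composite | in composite only |
| SAP 6.3 (analysis) | both of the above, full analysis set | composite only, full analysis set |
| Denominator limited to children scanned | not needed | not planned |

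**2. Reproduce the plan's own figure.** SAP Table 9-1 gives 95% Blyth-Still-Casella intervals for 0 to 4 events in 20. Recomputing them by refining the Clopper-Pearson limits matches all five rows to one decimal, including 0.0% to 15.4% for 0/20. The table is correct for 20 children who were all assessed.

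**3. Zero deteriorations among fewer scan pairs.** With m evaluable pairs and no event, the two-sided 95% Clopper-Pearson upper limit is U(m) = 1 − 0.025^(1/m). The documents do not give m, so these values are assumptions:

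- m = 20: 1 − 0.025^(1/20) = 16.8%
- m = 15: 1 − 0.025^(1/15) = 21.8%
- m = 10: 1 − 0.025^(1/10) = 30.8%

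The like-for-like comparison is 16.8% against 30.8%. The Blyth-Still-Casella limit for 20 is a little tighter (15.4%), so part of the gap between 15.4% and 30.8% is the choice of method. Within one age stratum of 10 children, if 5 had pairs, U(5) = 1 − 0.025^(1/5) = 52.2%.

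**4. Dilution of a non-zero count.** One deterioration in 20 enrolled children reads as 1/20 = 5%. If 10 were evaluable, the proportion among those assessed is 1/10 = 10%.

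**5. How likely is a count near zero?** The only event-rate input in the SAP is the prior for the daily log hazard of VTE recurrence (SAP 6.3.1 and 9.2; mean −6.6, precision 0.4). At its median the 30-day risk is 1 − exp(−30 × e^−6.6) = 4.0%. In 20 children:

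- expected events: 20 × 0.040 = 0.8
- P(0) = 0.96^20 = 44%
- P(0 or 1) = 0.96^20 + 20 × 0.04 × 0.96^19 = 81%

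Averaged over the whole prior, P(0) is 44% and P(0 or 1) is 65%. Asymptomatic deterioration would add to this risk, by an amount the documents do not state. At an assumed composite risk of 5%, P(0 or 1) is 74%; at 10%, 39%; at 15%, 18%. A count of 0 or 1 is therefore plausible but not assured.

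**The case against.** **The composite comes from the protocol.** The synopsis defines the secondary outcome as "Composite of all recurrent venous thromboembolism and asymptomatic deterioration on repeat imaging", so SAP 3.3 did not invent it. This is right, and the composite should stay. It does not replace the separate summary in Protocol 7.5.

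**The count can be derived.** Composite minus symptomatic recurrence gives the children with deterioration only, and SAP 4.1 promises frequency tables for categorical data. The subtraction works for that count, but the SAP does not plan it, it misses a child who has both, and it leaves the denominator at the full analysis set. The count of missing scans in SAP 4.3 helps, but it is not tied to the outcome, is not planned by age stratum, and does not cover scans that were done but could not be evaluated.

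**No interval is planned.** SAP 6.3 asks for incidence proportions only; the 15.4% is from the sample-size appendix. This also stands. The limits above show how a reader would interpret 0/20, not a planned output.

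**Stronger readings that the documents do not support.** A reader might infer that change in thrombotic burden is a stated objective, so that a one-directional endpoint is itself a fault. The objective names deterioration, and a yes/no reading fits it. A reader might also infer that graded readings are collected and then discarded. The documents say only that the committee assesses the scans; its procedures are in an adjudication manual that is not part of the protocol or SAP. Finally, a reader might expect a graded table to show whether clots resolve on rivaroxaban. The images submitted at screening are of the index event (Protocol 6.2), before at least 2 months of earlier anticoagulation, or 6 weeks if catheter-related (Protocol 4.2). No study scan is scheduled at Visit 1 or 2. In a single arm, improvement from that image cannot be credited to the study drug.

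**Conclusion.** The concern holds as a reporting and denominator gap. A separate secondary objective, which Protocol 7.5 says will be summarised, has no result of its own in the SAP, and the composite that contains it treats unscanned children as free of deterioration.

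The size depends on how many children have an evaluable pair. With 20 pairs the denominator makes no difference. With 10 of 20, the upper 95% limit for zero deteriorations rises from 16.8% to 30.8% (Clopper-Pearson), and any observed proportion doubles. The number of pairs is an assumption throughout, as is reading SAP 6.3 literally where it is silent on unscanned children.

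No sample size or error rate is affected, the primary bleeding analysis is untouched, and Table 9-1 is correct. The study is descriptive, so the consequence is a misleading degree of reassurance on one secondary objective, not a wrong test.

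**What to change.** **Main change.** In SAP 3.3, list asymptomatic deterioration on repeat imaging, as adjudicated, as a separate efficacy outcome. In SAP 6.3, report it overall and by age stratum, with children who have a repeat scan evaluable by the adjudication committee as denominator. Show the number not evaluable beside it, divided into no scan and scan not assessable. Keep the composite on the full analysis set, with a note saying how many children in it had no evaluable repeat scan.

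**Optional descriptive extension.** Tabulate the committee's category for each pair: normalised, improved, no relevant change, deteriorated, not evaluable. Name the reference image and its date, and state that improvement from the index image may reflect earlier anticoagulation. No efficacy conclusion should rest on the improved or normalised rows.

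**Cost.** One extra table and possibly one field on the adjudication form, depending on what the manual already records. No additional scan, reader or child is needed. The price for the sponsor is a smaller denominator and a less favourable upper limit.
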